In the somewhat likely event that the interaction between time point and treatment is not significant, we can directly test for treatment efficacy by comparing the effect of treatment on the treated vs. untreated structures. We expect that the model estimate for Treated or Untreated clause will be significant at p<0.05 level, favoring the treated clauses, demonstrating that treatment was effective and ruling out maturational effects.

$$\begin{aligned} \text{Likelihood of a Correct Production} &= \text{TestPoint} * \text{TreatedOrUntreated} \\ &\quad + (1|\text{item}) + (\text{clause type} |\text{subject}) \\ \text{Structural Sensitivity} &= \text{TestPoint} * \text{TreatedOrUntreated} \\ &\quad + (\text{clause type} |\text{subject}) \end{aligned}$$

Aim 2. Determine whether the influence of delivery method (illustrated syntax stories or recast therapy) on dose delivered (number of exposures to the target) is of sufficient magnitude that changes in child outcomes are observed when treatment is delivered by caregivers.

We will first determine whether dose differs across the two at-home conditions. We will carry out an unpaired two-tailed t-test comparing the estimated dose delivered for each condition. We anticipate that the two conditions will differ and that the distributions will show low degrees of overlap (p<.05, d>.5).

To test the key question in Aim 2, we will test for a dose by test point or dose by treatment condition by test point interaction for stories at home and recasts at home conditions. Well-matched groups at pretest will be evident if the two conditions do not differ at pre-test. If one treatment condition is more effective than the other, this should be evidenced by an interaction between test point and treatment contrast effects that are significant at the p<.05 level; if, as we hypothesize, dose is a critical component of this difference, a two- or three-way interaction between time and dose or between time, treatment and dose will be observed. We would interpret the two-way interaction as indicating that dose, rather than treatment is critical for obtaining the key outcomes. A three- way interaction suggests that the delivery method modifies the effectiveness of the total dose.

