$$\begin{aligned} \text{Likelihood of a Correct Production} &= \text{TestPoint} * \text{TreatmentCondition} * \text{EstimatedDose} \\ &\quad + (1|\text{item}) + (\text{clause type} |\text{subject}) \\ \text{Structural Sensitivity} &= \text{TestPoint} * \text{TreatmentCondition} * \text{EstimatedDose} \\ &\quad + (\text{clause type} |\text{subject}) \end{aligned}$$

In the event that the interaction between time point and treatment is not significant, we can directly test for treatment efficacy by comparing the effect of treatment on the treated or untreated structures. We expect that the model estimate for Treated vs. Untreated clause will be significant at p<0.05 level, favoring the treated clauses, demonstrating that treatment was effective and ruling out maturational effects.

$$\begin{aligned} \text{Likelihood of a Correct Production} &= \text{TestPoint} * \text{TreatedOrUntreated} \\ &\quad + (1|\text{item}) + (\text{clause type} |\text{subject}) \\ \text{Structural Sensitivity} &= \text{TestPoint} * \text{TreatedOrUntreated} \\ &\quad + (\text{clause type} |\text{subject}) \end{aligned}$$

Power Analysis for Production

Power analyses were carried out using Monte Carlo simulation (5,000 iterations) via SAS 9.4 and PROC GLIMMIX using residual pseudolikelihood estimation of a binary logistic mixed effects model with item responses (n=20) nested within tests (n=4 representing test point and clause type repeated measures) that are nested within children (n=120) who have been randomly assigned to treatment conditions, counterbalanced across the 2 clauses. Random effects are included for items within clauses, as well as four correlated child-level random effects (i.e., for each of the four repeated measures). A single model was used to estimate power in alignment with the overall design of the study in which children are randomly assigned to one of FOUR conditions. Power for the more focused models described above can be inferred from the power estimates for the treatment contrasts below. By adopting this randomization scheme and model design, we retain the ability to test unplanned contrasts that go beyond the planned analyses for the Aims if we so chose (e.g., recasts in the lab vs. recasts at home) in order to carry out secondary analysis associated with cost effectiveness, dose, or home environment.

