The influence of dose (Aim 2) was simulated by predicting different dose distributions for each condition. These distributions were simulated and then we randomly sampled from the distribution for each case. Hypothesized distributions of dose lead to substantial changes in the result, and thus we make our method of construction these distributions clear here. We assume that a minimum dose is achieved during the training visits (home condition) or by attending at least 1 session (lab condition) for all children. The two in-lab conditions are highly similar and both assume that 25% of participants attend between 1 and 12 sessions, 25% attend between 12 and 16, and the remainder have perfect attendance. This is a conservative estimate based on attendance data from our summer camp study.

The two at-home conditions require slightly more explanation. We assume for recasts that the first quartile has a dose of up to 1 recast/5 min for 60 min per week. The next quartile extends up to 1 recast/5 min for 120 min per week. The third quartile ranges up to a dose of 1 recast every 3 min for 120 min per week and the last quartile assumes target delivery. Similarly, syntax stories at home escalates from reading 1x/week to reading 2x/week to reading 4x/week (as asked) to reading 1 syntax story daily as the maximum. Several families in the pilot data for the syntax stories read the provided syntax stories daily.

Table 1. Hypothesized dose delivered by condition, in quartiles

	Recasts in lab	Stories in lab	Recasts at home	Stories at home
minimum	60	60	60	60
1st quartile	768	768	96	240
median	912	930	192	460
3rd quartile	960	960	320	960
maximum	1008	960	960	1680

Next the gain obtained from each dose was estimated by multiplying the dose provided by a value drawn from a uniform distribution ranging from .0005 to .006, to account for the fact that some children will be more responsive to any given dose than others. Finally, the gain was added to the pretest scores to yield posttest values. Simulations were checked to ensure that final post-test means and standard deviations for the treated structure were in line with estimates for post-test gains used for Aim 1 simulations. Planned statistical analysis were carried out over the simulated data and these simulations were repeated 1000 times.

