Simulations that include dose indicate power of .93 for models that include dose and time. Effects of treatment, dose, and power combined are not detectable because this estimation of dose confounds the distribution of dose with treatment delivery approach, as we hypothesize in the strategy. It suggests that three-way interactions will only be detectable if the delivery method modifies the benefit obtained from each exposure to the target form.

Power Analysis for Eye Tracking

Power analyses were carried out using G*Power (Faul, Erdfelder, Lang, & Buchner, 2007). Our preliminary data focused on eye-movements during a single test point, thus we do not have relevant estimates of fixation changes at multiple time points or following interventions. Consequently, we based our sample size on power analyses for production ($n=120$) and calculated the smallest changes in Structural Sensitivity that will be detectable with varying levels of power.

In our preliminary data ($n=15$), children with DLD revealed $M = 0.02$ and $SD = 0.17$ in the late window. With the proposed sample size, effect sizes of $d=.30$ will be detectable with 80% power, $d=.34$ with 90% power, and $d=.42$ with 99% power. These correspond to increases in Structural Sensitivity of $M=.05$, $M = .06$, and $M = .07$ respectively. For reference the TD children in our Preliminary Data have a Structural Sensitivity score that is $M=.29$ larger than that of the children with DLD. Based on this benchmark, improvements across time points that are 17-24% in magnitude would be detectable in the current design. This suggests that this study is adequately powered to detect relatively small changes in linguistically mediated fixations.

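### Aim 2 attributes a dose × treatment × test-point interaction to delivery method, but with linear dose and very different home-arm dose distributions, a shared levelling-off dose response can also raise that signal above 5%

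*Protocol*

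**What the plan says.** In the protocol's Analytic Approach, Aim 2, both outcomes (production accuracy and Structural Sensitivity) are modelled with the full product TestPoint × TreatmentCondition × EstimatedDose. Dose is one untransformed term. No curved dose term, linearity check or common-range analysis is stated. Smoothing is planned only for time within the eye-tracking series.

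Two readings are fixed in advance. For dose by time: "We would interpret the two-way interaction as indicating that dose, rather than treatment is critical for obtaining the key outcomes". For the three-way term: "A three- way interaction suggests that the delivery method modifies the effectiveness of the total dose".

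The same section expects the two home arms to receive different doses: "We anticipate that the two conditions will differ and that the distributions will show low degrees of overlap". Table 1, under Power Analysis for Production, gives minimum, quartiles and maximum of 60/96/192/320/960 for recasts at home and 60/240/460/960/1680 for stories at home. The story arm is described as rising "to reading 4x/week (as asked) to reading 1 syntax story daily as the maximum".

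In the Aim 2 simulation, each child's gain is the dose multiplied by a uniform draw between .0005 and .006, from the same distribution for both methods. The protocol reports power of .93 for dose with time and no detectable three-way effect. It concludes that "three-way interactions will only be detectable if the delivery method modifies the benefit obtained from each exposure to the target form".

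**The concern.** Two straight lines fitted to different stretches of one bent curve have different slopes. The home arms are expected to sit on different stretches of the dose axis. If each further exposure adds less once a child has had many, and does so equally for both methods, the story slope will be flatter because its doses lie further along the curve. A three-way coefficient is exactly that difference in slopes.

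The stated rule would then read a shared dose response as a property of the delivery method. The trial could report that stories give less benefit per exposure than recasts when benefit at any given dose is the same. That is the question Aim 2 sets out to answer. The simulation could not reveal the problem because it contained no curvature.

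**Working it through.** **The plan's own figure.** Drawing doses uniformly within the Table 1 quartiles gives these means:
- Recasts at home: (78 + 144 + 256 + 640)/4 = 279.5.
- Stories at home: (150 + 350 + 710 + 1320)/4 = 632.5.

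The standardised difference is about 0.96, consistent with the anticipated d > .5. The mean multiplier is (.0005 + .006)/2 = .00325, so mean gains are 279.5 × .00325 ≈ 0.9 and 632.5 × .00325 ≈ 2.1 points. These are close to the gains in the main power simulation: 4.0 − 3.0 = 1.0 and 5.5 − 3.0 = 2.5. Re-simulated dose-by-time power was about .97–1.00 against the stated .93. The residual variance and exact model are not given, so .93 can be neither confirmed nor refuted. Under linear dose the three-way term stayed near nominal, which agrees with the protocol.

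**Inputs for the check.**
- Mean home gain: (1.0 + 2.5)/2 = 1.75 points.
- Change-score SD from the protocol's SDs of 2.5 and 4.0 and correlation .90: √(6.25 + 16 − 2 × .90 × 2.5 × 4.0) = √4.25 = 2.06. A larger value of 2.5 was also used.
- 35 children per arm, the planned completers.
- Level .05, which the protocol states for the test point by treatment contrast. Its use for the three-way term is assumed.
- Dose curves: assumed, identical in both arms, scaled to the same mean gain.

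**Why the slopes part.** Take a plateau at 400 exposures. The share of families beyond it is .25 × (960 − 400)/(960 − 320) = 22% for recasts and .50 + .25 × (460 − 400)/(460 − 240) = 57% for stories. With gains of 1.20 and 1.77 points (mean about 1.5), the fitted slopes per 500 exposures are about 1.3 points for recasts and 0.5 for stories, although the curve is the same.

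**False three-way rate**, least squares on change scores, SD 2.06–2.5, mean gain 1.75:

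| Shared dose response | Linear-dose model |
|---|---|
| Linear | 5–6% |
| Smooth levelling-off | about 6–14% |
| Plateau at 400–960 | 10–22% |

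With a shared spline, or with doses limited to 960 or below, the rate returned to about 4–6%.

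**Closer to the planned model.** A random-intercept logistic model on treated items, 30–35 per arm, gave 4–9% under linear dose and 10–22% under shared levelling-off curves. A common quadratic dose × time term brought this to 4–9%. The bias does not shrink with sample size: at 200 per arm the rate was 34–68%, against 9% under linear dose. The coefficient pointed to a flatter slope for stories.

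**Power of the checks.** With a true doubling of recast benefit per exposure, three-way power was about 45–60% in the linear-dose model and about 28–41% in the checks. It was 22–33% if both checks had to be significant.

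**The case against.** The strongest reply is that the curve is invented. The protocol has no dose-response data and nothing in it points to a plateau at 400–600 exposures. It describes 600–1000 recasts as a typical effective dose, and most home-recast families in Table 1 fall below that. This stands as a limit on the size. It does not rescue the interpretation, because linearity is equally unsupported and the reading depends on it.

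The protocol's language is also soft. It says the interaction *suggests* modification, and the power section acknowledges that dose distribution and delivery approach are confounded. That is fair, but the word *only* still excludes the competing explanation.

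Four stronger readings are tempting and not supported:
- **That a levelling-off response will produce a three-way result.** At this sample size it does so in a minority of trials. Mild curvature (square root, logarithmic) stays close to nominal.
- **That the false rate is 21–39%.** Such figures arise with a mean gain of 3 points, well above the 1.75 the protocol implies for the home arms.
- **That the logit link alone breaks the test under the protocol's own generator.** The 15–17% seen there needs exact scores. With binomial item noise, as in the planned item-level analysis, it is 6–7%.
- **That the arms occupy separate dose ranges.** Both cover 60–960. Only their distributions differ.

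**Conclusion.** The point holds in a moderate form. A linear dose term, strongly different dose distributions and a fixed reading of the three-way term leave a shared non-linear dose response as an unaddressed explanation. At the protocol's own gains the false rate is roughly one to three times nominal for smooth curves and two to four times for plateaus. This rests on Table 1 doses being realised, on assumed curve shapes and mainly on a least-squares approximation, with a simplified logistic mixed model giving similar figures. No size was computed for Structural Sensitivity, although its Aim 2 formula has the same structure. The statement that only a method difference makes the interaction detectable is true if gain is linear in dose, and should say so. Nothing here shows that the dose response is in fact curved or that the planned model must be replaced.

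**What to change.** Keep the planned linear-dose model as the Aim 2 analysis. Pre-specify two repeats of the three-way test:
1. With a dose × TestPoint curve shared by both arms, either quadratic or a restricted cubic spline.
2. Within the dose range common to both arms, up to 960.

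Attribute a three-way result to delivery method only if the estimate keeps its direction and approximate size in both repeats, and define approximate size beforehand. Otherwise report a shared non-linear dose response as an alternative explanation. Reword the power section to say that its conclusion holds if gain is linear in dose.

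The cost is a few lines of code and text. A quadratic adds one shared dose × time term and a four-knot spline two. The range restriction sets aside about a quarter of story families, since their third quartile is 960. The larger cost is power (about 28–41% in the checks against 45–60%), which is why the repeats should qualify the interpretation and not have to be significant.

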We will also use generalized additive mixed models (GAMMs) to model longitudinal patterns in eyetracking data (i.e., looks to the agent) to examine and visualize timing of stimulus effects and changes in focus at key points during and after presentation of the prompt. GAMMs model fixations as an intensive time series (Cho et al., 2018, 2022) and allow identification of key points of separation. Moreover, the GAMMs models do not require prespecification of windows of time, providing more flexibility and sensitivity when modeling differences in eyetracking over time and between groups. The specification of the GAMMs models will mirror the GLMM equations below, except that smoothing functions will be used for an additional TIME predictor to fit a spline regression for each time series.

Aim 1. Determine the relative differences in the efficacy of illustrated syntax stories and recast therapy when treatment is dose controlled and delivered by highly trained SLPs in the laboratory.

We will first confirm that we achieved control of dose in the two in-lab conditions. We will carry out an unpaired two-tailed t-test comparing the estimated dose delivered for each condition. We anticipate that the two conditions will not differ and that the distributions will show high degrees of overlap ($p>.5$, $d<.3$).

To test the key question in Aim 1, we will compare the relative effect of treatment condition by testing for differences between the treatment effect estimates of stories in the lab and recasts in the lab conditions.

Well-matched groups at pretest will be evident if the two conditions do not differ at pre-test. If one treatment condition is more effective than the other, this should be evidenced by an interaction between test point and treatment contrast effects that are significant at the p<.05 level; if, as we hypothesize, the two conditions are equally effective there will be no significant interaction between test point and treatment. We are powered to detect an effect size difference of .35 (2 raw score points) or larger on production.

$$\begin{aligned} \text{Likelihood of a Correct Production} &= \text{TestPoint} * \text{TreatmentCondition} \\ &\quad + (1|\text{item}) + (\text{clause type} |\text{subject}) \\ \text{Structural Sensitivity} &= \text{TestPoint} * \text{TreatmentCondition} \\ &\quad + (\text{clause type} |\text{subject}) \end{aligned}$$

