Test scores were simulated based on means and standard deviations of pretest and posttest scores from a previous study. Pretest scores for both clauses were sampled from a Normal distribution with $M=3.0$ and $SD=2.5$, rounding to the nearest integer, with a minimum score of 0 and maximum score of 7 items correct (corresponding to the >40% correct study eligibility criteria). Posttest scores for untreated clauses were sampled from a Normal distribution with a correlation of .90 with pretest scores and $M=3.0$ and $SD=2.5$, rounding to the nearest integer, with a minimum score of 0. Posttest scores for treated clauses were sampled from a Normal distribution with a correlation of .90 with pretest scores, rounding to the nearest integer, with a minimum score of 0, and $M=5.5$ and $SD=4.0$ for the syntax stories at home condition ($ES=+1.0$), $M=4.0$ and $SD=4.0$ for the parent recasts condition ($ES=+0.4$), $M=6.0$ and $SD=3.5$ for the syntax stories in the lab condition ($ES=+1.2$), and $M=8.0$ and $SD=3.5$ for the lab recasts condition ($ES=+2.0$).

Based on the above effect size estimates, power for detecting main effects in Aim 1 exceeds .95 for the syntax stories at home, syntax stories in the lab, and lab recasts. Power is .61 for detecting main effects of parent recasts (i.e., the effect of parent recasts would need to exceed .50 to be detected with 80% power). Power for treatment effect contrasts is .75 to detect differences in syntax stories at home and parent recasts effects, .90 to detect differences in parent recasts and syntax stories in the lab effects, and .99 to detect differences in parent recasts and lab recasts effects. Other contrasts (e.g., syntax stories at home vs. syntax stories in the lab) have power less than 80% if the expected effect sizes hold true (i.e., +1.0 vs. +1.2); differences in effects would need to exceed 0.35 logits (2 raw score points) in order reach statistical significance with 80% power.

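### The only comparison with the untreated clause pools stories and recasts and is written only for a non-significant interaction, so it cannot support an efficacy claim for either arm

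*Protocol*

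**What the plan says.** The Treatment section assigns children to recasts or syntax stories, each given by a clinician or a caregiver. There is no untreated arm. Each child is treated on one clause type and not on the other, and this is counterbalanced.

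Under Analytic Approach, the main production model for Aim 1 crosses test point with treatment condition. Aim 2 adds estimated dose. Neither has a term for treated versus untreated clause. An arm difference is to be shown by an "interaction between test point and treatment contrast effects that are significant at the p<.05 level".

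The untreated clause enters through a second model in each aim, which crosses test point with treated-or-untreated clause and has no treatment-condition term. It is introduced in Aim 1 by "In the somewhat likely event that the interaction between time point and treatment is not significant, we can directly test for treatment efficacy" and in Aim 2 by "In the event that the interaction between time point and treatment is not significant, we can directly test for treatment efficacy". Its expected result is described as "demonstrating that treatment was effective and ruling out maturational effects". The same pair of models is written for Structural Sensitivity.

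Power Analysis for Production gives power arm by arm: "power for detecting main effects in Aim 1 exceeds .95 for the syntax stories at home, syntax stories in the lab, and lab recasts", and "Power is .61 for detecting main effects of parent recasts".

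**The concern.** The second model answers whether the treated clause gained more than the untreated clause, averaged over two different treatments. This creates two problems.

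- **Pooling.** Failure to detect a difference between arms is not evidence that both work. If one arm is active and the other inert, the average can still differ from zero, and the plan would state efficacy without saying for which treatment.
- **Conditioning.** If the arms do differ, the plan can rank them, but it writes out no comparison showing that the lower one beats maturation. A pre-post gain within an arm cannot fill that gap: the children are 4-7 years old, outside therapy is allowed, and the plan itself names maturation as the explanation to be excluded.

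The arm most exposed is caregiver recasts. The section on protections against risk says the investigators expect it to be less effective, and it has the lowest stated power. The plan quotes power for four per-arm effects, but its analysis section has no model that estimates them against the untreated clause.

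**Working it through.** **Inputs (Power Analysis for Production).** Parent recasts: effect 0.4, power .61, and .50 needed for 80% power. Stories at home: effect 1.0. At-home contrast: power .75 for a difference of 1.0 - 0.4 = 0.6. The power model has n = 120, so 30 per arm. Two-sided alpha of .05 is assumed.

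**1. Reproduce the plan's figure.**
Per-arm SE = 0.4 / (1.960 + 0.279) = 0.179.
Detectable effect at 80% power = 0.179 × (1.960 + 0.842) = 0.50, as stated.

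**2. SE of the contrast between two arms.**
From the per-arm SE: 0.179 × √2 = 0.253.
From the stated .75: 0.6 / (1.960 + 0.674) = 0.228.
Both are carried forward as a range.

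**3. Joint probability with one null arm.** Let the other arm have effect e and let c be the contrast SE. The difference test has z = e/c. The pooled estimate has mean e/2 and SE c/2, so its z is also e/c. With equal SEs the sum and difference of the arm estimates are independent. If p is the power at z = e/c, then

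P(interaction not significant and pooled test significant) ≈ (1 - p) × p.

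This cannot exceed 0.25.

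| e | p (c = 0.228) | joint | p (c = 0.253) | joint |
|---|---|---|---|---|
| 0.4 | .42 | 24% | .35 | 23% |
| 0.5 | .59 | 24% | .51 | 25% |
| 0.6 | .75 | 19% | .66 | 22% |
| 0.8 | .94 | 6% | .89 | 10% |
| 1.0 | .99 | 1% | .98 | 2% |

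A per-arm test at two-sided .05 would favour a null arm in about 2.5% of trials. With both arms null, the joint rate under the plan's rule is about 2.3%.

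**4. At the planned home effects (1.0 and 0.4).** The pooled effect is 0.7 with SE c/2 = 0.114 to 0.126, so z is about 5.5 to 6.1. The pooled test is significant in nearly every trial, although parent recasts alone has power .61. The pooled result therefore says almost nothing about that arm.

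**5. Score-level check.** Scores were simulated from the stated means, SDs and .90 correlation, with 30 and 35 per arm, on raw and empirical-logit scales. The between-clause correlation is not given and was taken as 0.5. With the interaction tested on treated-minus-untreated gain, the joint rate was 16-18% at effect 0.4, 6-22% at 0.6 and 0-7% at 1.0. With the interaction tested on treated-clause gain only, it was 5-13%, 1-10% and under 1%.

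**6. The dose term in Aim 2.** Steps 2-4 leave dose out, but the Aim 2 model includes it. Child-level gains were simulated from the Table 1 quartiles and the stated uniform multiplier (.0005 to .006), with an assumed residual SD of 1 raw point and dose mean-centred. The time-by-treatment term was significant in 68-75% of trials without dose and in about 5% with dose in the model.

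**The case against.** **Efficacy against maturation is not an aim.** Aim 1 concerns relative efficacy and Aim 2 concerns dose, and the efficacy statement names no arm. This is fair. But the plan does state an efficacy conclusion, without qualification, from a model that cannot say which treatment earned it.

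**The wording is permissive.** The plan says the team can run this test, speaks of change over time for each condition, and describes a four-condition power model that could yield per-arm effects. A reader might infer that per-arm effects are never tested. The text does not go that far; it supports only that no per-arm treated-versus-untreated test is written out. That still matters, because the document is marked as including the statistical analysis plan and gives its model equations.

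**The probabilities are near their ceiling.** A reader might infer that an inert arm would be called effective in a quarter of trials. The 19-25% is the peak of p(1 - p), reached only if one arm is null and the other has an effect of 0.4-0.6. The plan assumes neither for the home arms, and against its assumed 1.0 for home stories the figure is 1-2%.

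**The contrast power of .75 does not describe the Aim 2 trigger.** A reader might infer that about 75% of trials would leave home recasts without an efficacy test. That power comes from a model without dose, while the Aim 2 interaction is tested with dose included. Under the plan's own dose assumptions it would then seldom be significant, and the pooled model would usually run. So in Aim 2 pooling is the main fault and conditioning the lesser one.

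**Conclusion.** The concern holds in limited form. The comparison with the untreated clause pools two treatments, has a non-significant interaction as its only stated trigger, and is read as efficacy without qualification. The per-arm effects for which power is quoted have no corresponding written test.

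With one null arm, the chance of a non-significant interaction together with a significant pooled test is at most about 25%: 19-25% if the other arm has effect 0.4-0.6, 6-10% at 0.8, and about 1-2% at 1.0. These figures rest on SEs implied by the stated power at 30 per arm (35 completers per arm are planned), two-sided .05, a normal approximation, the production outcome, and no dose term. The score-level check is mostly lower and more variable.

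Overall type I error is not inflated. The error at stake is crediting a treatment with an effect that the other arm produced. The plan's SAS simulation was not rerun, and none of its stated powers is called wrong.

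**What to change.** In each aim, fit test point × treated-or-untreated × treatment condition whatever the arm interaction shows. Report the treated-minus-untreated gain with its 95% CI separately for each arm, and claim efficacy only for arms whose own interval excludes zero. Keep the pooled estimate as a secondary summary, described as an average over the two treatments. Apply the same change to Structural Sensitivity.

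No new data are needed; only analysis wording changes. The price is lower precision per arm than for the pooled estimate. For parent recasts that is the .61 power the plan already states, and for the other three arms the stated power exceeds .95.
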